Study Protocol

Exploring different composite definitions of responders and non-responders to biologic treatment for severe asthma (FULL BEAM)

Date:

1 November 2022

Client contact:

[name]

Chief Investigator:

[name], Professor of Primary Care Respiratory Medicine and OPRI Director

[contact]

Office number: [name]

Skype ID: [name]

Email: [contact]

Project Coordinator:

[name], Research & Operations Director Observational & Pragmatic Research Institute

Office address: [name]

Direct number: [contact]

Email: [contact]

ISAR Steering Committee Lead:

TBD

Study Sponsor:

AstraZeneca

Primary Contact:

[name] [[contact]]

TITLE	Exploring different composite definitions of responders and non-responders to biologic treatment for severe asthma	
Subtitle	NA	
Protocol version number	v1.3	
Medicinal product	Not applicable	
Product code	Not applicable	
Marketing authorisation holder	Not applicable	
Marketing authorisation number	Not applicable	
Study aims and objectives	Aim: Examine different composite definitions of response/remission and characterize patients according to different definitions in a real-world setting to identify composite measures most useful to assess response/remission in clinical practice Objective 1: To define the study population Objective 2: To quantify levels of response and characterize patients by levels of response Objective 3: To quantify aspects of asthma clinical remission and characterize patients according to different definitions	
Countries of study	Argentina, Australia, Bulgaria, Canada, Colombia, Denmark, Greece, India, Ireland, Italy, Japan, Kuwait, Mexico, Poland, Portugal, Saudi Arabia, South Korea, Spain, Taiwan, UAE, UK, USA	
Author(s)	[name]	

Table of Contents

List o	f Abbreviations	5
1.0	Background	6
2.0	Study Aims and Objectives	12
2.1	Study Aims	12
2.2	Study Objectives	12
3.0	Study Design	13
4.0	Study Population	15
4.1	Data Sources	15
4.2	Inclusion and Exclusion Criteria	15
5.0	Study Variables and Study Outcome Definitions	17
5.1	Individual response/remission domains	17
5.1.1	L Exacerbation rates	17
5.1.2	2 Long-term OCS use	17
5.1.3	3 Asthma symptoms control	18
5.1.4		
5.2	Composite definitions of response/remission	
5.2.2		
5.2.2		
5.3	Analytical variables	
6.0	Statistical Analysis	25
6.1	Software	
6.2	Sample size	
6.3	Analysis for objective 1	
6.4	Analysis for objective 2	
6.5	Analysis for objective 3	
7.0	Regulatory and Ethical Compliance	29
8.0	Data Dissemination	2 9
9.0	Advisory Group	30
10.0	Research Team	31
11.0	Timelines	32
12.0	References	33

LIST OF ABBREVIATIONS

Abbreviation or special term	Explanation	
ACQ	Asthma control questionnaire	
ACT	Asthma control test	
ADEPT	Anonymised Data Ethics & Protocol Transparency	
AQLQ	Asthma quality of life questionnaire	
BD	Bronchodilator	
BMI	Body mass index	
eCRF	Electronic clinical record form	
EMR	Electronic medical record	
FeNO	Fractional exhaled nitric oxide	
FEV ₁	Forced expiratory volume in the first second	
GETE	Global Evaluation of Treatment Effect	
GINA	Global INitiative for Asthma	
IgE	Immunoglobulin E	
IL13	Interleukin 13	
IL4	Interleukin 4	
IL5	Interleukin 5	
IL5R	Interleukin 5 receptor	
ISAR	International Severe Asthma Registry	
ISC	ISAR Steering Committee	
JAQoL	Jobs and quality of life	
LABA	Long-acting bronchodilator inhalers	
LAMA	Long-acting muscarinic antagonist	
LTOCS	Long-term oral corticosteroids	
LTRA	Leukotriene receptor antagonist	
NICE	National Institute for Health and Care Excellence	
OCS	Oral corticosteroids	
OPC	Optimum Patient Care	
OPRI	Observational and Pragmatic Research Institute	
PEF	Peak expiratory flow	
RCT	Randomized control trial	
REG	Respiratory Effectiveness Group	
T2	Type 2 inflammation	
TSLP	Thymic stromal lymphopoetin	

1.0 Background

Asthma is a chronic, usually life-long inflammatory disorder of the airways affecting approximately 358 million people worldwide (1). Despite recent advances in treatment options, as many as 50% of affected adults have persistent symptomatic asthma and about 3-10% have severe asthma (2-4). Severe asthma is defined by the Global Initiative for Asthma (GINA) as asthma that is uncontrolled despite maximal optimized therapy and treatment of contributory factors, such as poor inhaler technique and adherence, or that worsens when treatment is decreased (5). Severe asthma results in increased morbidity such as impaired quality of life, loss of pulmonary function and a higher rate of exacerbations and hospitalization (4, 6). This translates into a significant financial burden with an estimated expenditure of €33.9 billion in Europe in 2011; approximately half of which is due to significant work impairment and productivity loss as a result of poor asthma control (7, 8).

In addition to maintenance therapy, long-term treatment with oral corticosteroids (OCS) or frequent, short bursts of OCS are commonly prescribed during an asthma exacerbation to treat the increased inflammatory response which is typically associated with an exacerbation (9, 10). This treatment plays an important role in the long-term severe asthma management and is effective for rapid relief of symptoms to prevent subsequent emergency admission. However, it has been associated with increased morbidity and related healthcare costs (11-13). Specifically, there is a dose-response, risk-association between long-term OCS use and adverse events, such as the onset or progression of osteoporosis, pneumonia, cardio-/cerebrovascular diseases, cataracts, sleep apnoea, depression/anxiety or weight gain (14). Fortunately, patients that are dependent on long-term OCS are eligible to receive novel, monoclonal antibody therapies as clinicians attempt to reduce exacerbation risk and minimize patients' exposure to OCS (10, 15).

The first monoclonal antibody was anti-immunoglobulin E (anti-IgE), which has been introduced more than twenty years ago. This spurred a rapid shift towards targeted therapies for severe asthma, particularly directed at the interleukin-5 inflammatory pathway (anti-IL5) and, more recently, to the interleukin-4 and 13 inflammatory pathways (anti-IL4/IL13). These modalities of therapy have been repeatedly found to be effective in improving asthma-related clinical outcomes such as exacerbation rates, OCS use, asthma symptoms control and lung function (16-28) (Table 1). Although many randomized controlled trials (RCTs) have demonstrated the clinical efficacy and safety of these monoclonal antibodies, their strict inclusion criteria may mean the obtained results only apply to a proportion of the severe

asthma target population. Therefore, the results of these studies may not necessarily reflect the individual response to biologics of patients with severe asthma in a real-world setting.

The response to biologic therapies is variable between patients (27, 29). Biomarkers are used to determine the biologic treatment initiation (15), while the improvements in clinical endpoints such as exacerbation and long-term OCS dose reduction are more pronounced in high baseline blood eosinophil groups (i.e. ≥300 cells.µL⁻¹) than low eosinophil groups (i.e. <300 cells.µL⁻¹) in studies that performed the comparisons (16, 17, 30). Besides the biomarkers, pooled analyses of two phase III clinical trials have shown that a history of hospitalization, LABA use, higher inhaled corticosteroid dose, higher FeNO and lower FEV1 levels at baseline predicted better response to anti-IgE treatment in terms of percentage reduction in exacerbations (31, 32). In addition, pre-treatment daily prednisone requirement, sinus disease, and late-onset asthma diagnoses were the strongest predictors of suboptimal response to anti-IL5 treatment (33). However, these pre-treatment characteristics do not fully predict future response (34) and other factors, for instance BMI, socioeconomic status, age, and comorbidities, such as nasal polyposis, allergic rhinitis and chronic rhinosinusitis may also influence response (27, 35, 36). Therefore, gaining a better understanding of these factors could aid in the early identification of patients who are likely to receive benefit from monoclonal antibody therapy.

A universal definition of treatment response remains to be agreed upon. The National Institute for Health and Care Excellence (NICE) has recognized a reduction of exacerbation rate of at least 50% or a clinically reduced dose of long-term OCS as an adequate response, assessed up to 12 months after biologic therapy initiation (37). Currently, physician knowledge or tools like Global Evaluation of Treatment Effect (GETE) (38) are often used to evaluate patient response or treatment continuation. There have been a few real-world studies that have attempted to define responders based on post-biologic improvements in a variety of clinical and functional endpoints with reduction in exacerbations, OCS dose and asthma symptoms control being the most common domains (Table 2). In these studies, the proportion of patients with response ranged from 64% to 83% and time of response assessment ranged from 12 weeks to 1 year (32, 39-44). Furthermore, Delphi-based studies have attempted to operationally define responders and/or super-responders (Table 3). Upham et al. (45) surveyed eighty-one health care professionals (94% pulmonologists or allergists) from 27 countries via a multi-stage Delphi process to compose a super-responder definition. The international consensus-based, definition of super-responder encompassed an improvement of 3 or more domains (minor or major criteria) assessed over a 12-monthperiod. Perez de Llano et al. (46) developed a score ranging from 0 (worsening) to 100 (best

possible response) based on weighted response in four domains (severe exacerbations, OCS use, symptoms as evaluated by Asthma Control Test (ACT), and bronchial obstruction as assessed by FEV₁ percent predicted).

More recently, Menzies-Gow et al. have proposed a framework for asthma remission for all levels of disease severity as a treatment target based on relevant medical literature in other chronic inflammatory diseases such as rheumatoid arthritis and ulcerative colitis, as well as a modified Delphi survey to garner expert consensus (47) (see Table 3). While previous studies aimed to classify response to treatment by quantifying improvement from pre- to post-biologic initiation therapy, the concept of remission relates to a state or period with low to no disease activity. Its definition in the field of asthma and whether it should be the goal of initiating biologic therapy remains under debate.

Despite the emergence of common domains of treatment response, there is little agreement on clinically useful criteria for identifying real-world responders. To identify responders, clinically relevant markers of treatment response that are unequivocally applicable to all biologics must first be chosen, and then different levels of response characterized and compared. Furthermore, the emerging concept of remission in severe asthma patients remains to be explore in a real-world setting. The International Severe Asthma Registry (ISAR), the largest, real-life data repository of severe asthma cases from 24 countries, offers a unique opportunity to explore response and remission, and characterize patients with across groups using different composite definitions of both.

Table 1. Summary of findings of anti-IL5 and anti-IgE therapies from high quality RCTs*

Study	Design	Exacerbation rate	mOCS Dose	Pre-bronchodilator FEV ₁	ACQ and AQLQ
Nair P, et al. 2017 (16)	Benralizumab (Anti-IL5) 28-week, n = 220			û 210mL baseline û 105-112mL placebo	
Bleecker ER, et al. 2016 (17)	Benralizumab (Anti-IL5R) 48-week, n = 1205	⊕62-76% vs baseline ⊕21-68% vs placebo²		û 120-398mL baseline² û 106-159mL placebo	
Chupp GL, et al. 2017 (18)	Mepolizumab (Anti- IL5) 24-week, n = 551				
Castro M, et al. 2015 (19)	Reslizumab (Anti-IL5) 52-week, n = 953			û 220mL baseline û 110mL placebo	
Ortega HG, et al. 2014 (20)	Mepolizumab (Anti- IL5) 32-week, n = 576	 			
Pavord ID, et al. 2012 (21)	Mepolizumab (Anti- IL5) 52-week, n = 621	 ♣ 57-67% vs baseline ♣ 48-52% vs placebo 		û 115-140mL baseline û 15-81mL placebo	
Hanania NA, et al. 2011 (22)	Omalizumab (Anti-IgE) 48-week, n = 850	♣ 67% vs baseline♣ 25% vs placebo			
Lanier B, et al. 2009 ⁴ (23)	Omalizumab (Anti-IgE) 28-week, n = 627				
Holgate ST, et al. 2004 (24)	Omalizumab (Anti-IgE) 52-week, n = 246		 ♣ 73.8% baseline³ ♣ 23% placebo³ 	û 89-116mL post-BD placebo	
Soler M, et al. 2001 (25)	Omalizumab (Anti-IgE) 28-week, n = 546		 		
Busse W, et al. 2001 (26)	Omalizumab (Anti-IgE) 28-week, n = 525		⊕ 75% baseline (ICS) ⊕ 25% baseline placebo (ICS)	û Predicted FEV₁ 4.3% baseline û Predicted FEV₁ 2.9% placebo	

Change % from baseline (absolute difference pre- vs post-biologic) and change % vs placebo (absolute difference drug arm vs placebo). ACQ and AQLQ MCID 0.5 points. Ranges (e.g. 55-70%) reflects the differences in dosage, frequency and baseline biomarkers between the groups of patients.

*Based on assessment from Cochrane review reports (48, 49).

¹While maintaining asthma control; ² Eosinophils ≥300 group exacerbation reduction of 45-51% and FEV₁ increase of 345-398mL; ³ Fluticasone ≥50% dose reduction; ⁴ Study quality unknown.

Table 2. Results of key previous studies measuring responders and non-responders to anti-IL-5 and anti-IgE therapy

					Responder Defini	tion Endpoints		
Study	Study Design & Population	% Responders & Time	Exacerbations	OCS Dose	Asthma Control	Quality of Life/Assessment	Lung Function	Other
NICE, 2017, Mepolizumab and Reslizumab	Guidelines	at 12 months	≥50% reduction	Clinically significant reduction	Maintain asthma control			
Bousquet J, 2004, Omalizumab (32)	Post-hoc RCT, n = 1070, 55% females, 39 y.	64% at week 16	No exacerbations		Reduction ≥1 level	Increase ≥1 JAQoL	Increase PEF of ≥15	≥1 puffs of rescue medication
Kavanagh JE, 2020, Benralizumab (50)	Retrospective review, n = 130	86% at week 48	≥50% reduction	OR ≥50% reduction				
Kavanagh JE, 2020, Mepolizumab (42)	Retrospective review, n = 99, UK	72.7% responders and 28.3% super- responders at 1-year	≥50% reduction	≥50% reduction (if on)				
Kavanagh JE, 2018, Mepolizumab (40)	Retrospective review, n = 35, 49% females, 55.8y.	77% at week 12		≥50% reduction				
Niven RM, 2016, Omalizumab (39)	Mixed non- interventional, n = 258, 65% female, 44.7y.	82.4% responders at week 16	•	essment at week				
Braunstahl GJ, 2013, Omalizumab (43)	Observational registry, n = 943, 65% females, 45y.	64.2% responders at week 16				GETE ² at week 16		
Drick N, 2018 Mepolizumab (41)	Retrospective review	76% responders at 6 months				Improvement of subjective condition ³	Increase FEV1 12% or≥200 ml	Reduction of blood eosinophils
Gibson PG, 2016, Omalizumab (44)	Web-based registry	83% responders	1000		≥0.5 in ACQ-5			

¹ Based on NICE and SMC criteria which includes exacerbation and OCS dose reduction.

² During interview patients were asked by the physician whether their subjective condition under therapy had improved or worsened (yes / no question), patients asked to consider asthma-related symptoms, quality of life (QoL), number of exacerbations and improvement of physical fitness.

³ Global evaluation of treatment effectiveness (GETE) (38).

Table 3. Summary of Delphi studies defining responders to biologic therapy

			Domains (criteria in order	of importance for multiple options)
Study	Design	Exacerbation	OCS use	Asthma Control	Lung Function
Upham et al. (45)	Super-responder: meet 3 criteria (at least 2 major criteria)	Minor: ≥75% reduction Major: Elimination	Minor: N/A Major: Cessation or weaning of long-term OCS	Minor: Well controlled asthma Major: 2x MCID improvement	Minor: FEV1 500ml improvement Major: N/A
Perez et al. (46)	A response score from 0 to 100 via multiple domains	<50% reduction ≥50% reduction, but ≥1 severe exacerbations No severe exacerbations	<50% reduction Reduction ≥50% but <100% Withdrawal	≥ 3 points for ACT Total score ≥20	Pre-BD FEV1 increase ≥ 100mL FEV1 ≥80% of predicted
Menzies-Gow, Bafadhel et al. 2020 (47)	Framework for asthma remission as a treatment target. Time period ≥12 months	(HCP and patient agreement regarding remission)	No use of systemic corticosteroid therapy	No asthma symptoms	Optimization and stabilization of lung function

2.0 Study Aims and Objectives

2.1 Study Aims

In a real-world setting examine different composite definitions of response and remission following initiation of biologic therapy in adults with severe asthma in relation to patient characteristics before therapy initiation to identify composite measures most useful to assess response and remission in clinical practice.

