5.0 Study Variables and Study Outcome Definitions

While clinical remission will be assessed in all patients irrespective of their status prebiologic initiation, response can only be assessed in patients impaired when initiating the treatment. Impairment will be defined for each domain independently as: 1) exacerbations: ≥2 exacerbations in the year preceding biologic initiation; 2) long-term OCS use: patients receiving long-term (daily) OCS at biologic initiation; 3) asthma symptoms control: partly or uncontrolled patients at biologic initiation, based on GINA 2020 asthma symptoms control categories (5); 4) lung function: patients <80% FEV1 predicted pre-biologic initiation.

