5.2 Composite definitions of response/remission

5.2.1 Response

Eligibility criteria for impairment at biologic initiation and individual domain response definitions described in section 5.1 will be applied for the composite definitions of response. Levels of response will be defined for each composite definition by the number of single domain response criteria met as follows:

1) Exacerbation rates and long-term OCS use

Eligibility criteria: Patients with ≥2 exacerbations in the year preceding biologic initiation & receiving long-term OCS at biologic initiation

Response levels:

- Level 0: meeting none of the response criteria
- Level 1: meeting 1 of the response criteria
- Level 2: meeting both response criteria

2) Exacerbation rates, long-term OCS use, and asthma symptoms control

Eligibility criteria: Patients with ≥2 exacerbations in the year preceding biologic initiation

& receiving long-term OCS at biologic initiation

& being partly or uncontrolled at biologic initiation

Response levels:

Level 0: meeting none of the response criteria

Level 1: meeting 1 of the response criteria

· Level 2: meeting 2 response criteria

Level 3: meeting all 3 response criteria

3) Exacerbation rates, long-term OCS use, asthma symptoms control, and lung function*

Eligibility criteria: Patients with ≥2 exacerbations in the year preceding biologic initiation

& receiving long-term OCS at biologic initiation

& being partly or uncontrolled at biologic initiation

& having FEV1 <80% predicted at biologic initiation

Response levels:

• Level 0: meeting none of the response criteria

Level 1: meeting 1 of the response criteria

• Level 2: meeting 2 response criteria

• Level 3: meeting 3 response criteria

• Level 4: meeting all 4 response criteria

In order to explore composite definitions of response in non long-term OCS users, the variables defined above will be computed in this subgroup of patients after excluding the reduction in long-term OCS daily doses, ie 1) reduction in exacerbations and improvement in asthma symptoms control; and 2) reduction in exacerbations, improvement in asthma symptoms, and improvement in lung function. Other combinations of composite definitions of response (eg, improvement in asthma symptoms control and improvement in lung function alone) will also be explored.

^{*} The response criteria for improvement in lung function will primarily be an increase of at least 100mL in FEV1. Other criteria will be explored.

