5.2.1 Remission

Composite definitions of remission will not impose pre-biologic impairments in any domains. The strict definitions will allow no exacerbation over the year following biologic initiation and no long-term OCS use at approximately 1 year after biologic initiation. The relaxed definitions will allow up to 1 exacerbation (not requiring hospitalisation) and up to 5mg/day of long-term OCS (a dose that can be used in patients who have adrenal insufficiency). Asthma symptoms control and lung function criteria will be progressively added as follows:

1) Exacerbation rates and long-term OCS use:

Strict definition:

no exacerbation in the year following biologic initiation

& no long-term OCS use at ~1 year following biologic initiation

Relaxed definition:

- ≤1 exacerbation (not requiring hospitalisation) in the year following biologic initiation
- & long-term OCS ≤5mg/day at ~1 year following biologic initiation

2) Exacerbation rates, long-term OCS use, and asthma symptoms control:

Strict definition:

- no exacerbation in the year following biologic initiation
- & no long-term OCS use at ~1 year following biologic initiation
- & partly/well controlled at ~1 year following biologic initiation

Relaxed definition:

- ≤1 exacerbation (not requiring hospitalisation) in the year following biologic initiation
- & long-term OCS ≤5mg/day at ~1 year following biologic initiation
- & partly/well controlled at ~1 year following biologic initiation

3) Exacerbation rates, long-term OCS use, asthma symptoms control, and lung function:

Strict definition:

no exacerbation in the year following biologic initiation

- & no long-term OCS use at ~1 year following biologic initiation
- & partly/well controlled at ~1 year following biologic initiation
- & FEV1 ≥80% predicted at ~1 year following biologic initiation

Relaxed definition:

- ≤1 exacerbation (not requiring hospitalisation) in the year following biologic initiation
- & long-term OCS ≤5mg/day at ~1 year following biologic initiation

& partly/well controlled at ~1 year following biologic initiation

& FEV1 ≥80% predicted at ~1 year following biologic initiation or stable lung function

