6.2 Sample size

As of 21 July 2022, a total of 5,961 patients who initiated biologics are recorded in ISAR.

All patients (objective 3)

Preliminary numbers of patients that will enter the remission analysis (objective 3) are presented in Figure 2. While pre-biologic status for the asthma-related outcomes is not a pre-requisite for the description of remission status, patients with no pre-biologic data overall will be excluded from the analysis as an important part of the project will be to characterize the patients at biologic initiation.

[figure not shown]

Figure 2. Preliminary flowchart of data availability for patients who initiated any type of biologics as of 21 July 2022. Exclusions are sequential from top to bottom.

In patients impaired at biologic initiation, by single domains and composite definitions of response (objective 2)

Table 5. Preliminary sample size of impaired patients at biologic initiation (numbers presented are patients who were impaired at biologic initiation and with available data at follow-up).

Domains	N
1. Exacerbations(≥2 exacerbation in the year preceding biologic initiation)	1,392
2. Long-term OCS dose (receiving long-term OCS at biologic initiation)	475
3. Asthma symptoms control (uncontrolled or partially controlled at biologic initiation)	1,360
4. Lung function (FEV ₁ <80% predicted at biologic initiation)	1,179
1+2	313
1+2+3	264
1+2+3+4	134

6.3 Analysis for objective 1

Objective 1 aims at describing the study population used in objectives 2 and 3. To this end, the pre-biologic asthma-related outcomes will first be described individually and in composite variables. For individual asthma-related outcomes, both continuous and categorical variables will be used. The categories will be based on the eligible criteria used for impairment:

- Exacerbations: ≥2 versus <2
- Long-term OCS use: yes/no
- Asthma symptoms control: partly or uncontrolled versus well controlled
- Lung function: ≥80% versus <80% FEV1 predicted

The distributions will be compared between initiated biologic class using t-tests, Kruskall Wallis tests, or Person's Chi-squared tests as appropriate. The distribution of pre-biologic asthma related outcomes will also be compared between countries (or geographic regions in case of small sample size).

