Patient characteristics (see Table 4) will also be described and compared univariately between the initiated biologic classes using appropriate statistical tests based on variable type and distribution.

6.4 Analysis for objective 2

Descriptive analysis

The proportion of patients responding to biologics as defined in section 5 will be computed overall and by biologic classes, for each individual domain and composite definition of response.

Patient characteristics will be described by levels of response using means, standard deviations, medians and interquartile ranges for continuous variables and numbers and percentages for categorical variables.

Trajectories from pre- to post-biologic status will also be described as cross-tabulations, by single domains and composite definitions.

Since the requirements for biologic initiation vary by countries, the above analysis will be stratified by pre-biologic status (eg, no exacerbation, no long-term OCS use, alone or in combination), overall and by country/geographic regions.

Association analysis (composite definitions)

Univariate analysis:

- The association between patient characteristics, including country/geographic region (see Table 4), and ordinal response levels will be tested by fitting ordinal logistic regressions using response levels as the outcome variable and each patient characteristic individually. Significance will be tested through log-likelihood ratios.
- Where the proportionality of odds assumption does not hold in the ordinal logistic regressions, binary logistic regressions will be used instead comparing extreme levels to all other levels of response.
- The comparisons will be performed overall and for each class of biologics separately.

• Multivariate analysis:

- We will use logistic regression techniques in a similar fashion as above, fitting
 in the same model the patient characteristics that are significant (p<.05) in the
 univariate analysis.
- o The models will be fitted overall and for each class of biologics separately.
- Optionally, a single model will be fitted adding biologic class in the model together with patient characteristics.

6.5 Analysis for objective 3

Descriptive analysis

The proportion of patients in different definitions of remission at follow-up as defined in section 5 will be computed overall and by biologic classes, for each individual domain and composite definition of response.

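### The three main response composites are computed in nested but different populations (313, 264, 134), and section 6.4 plans no comparison in a shared one

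*Protocol*

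**What the plan says.** Section 2.1 gives the purpose of examining several composites as "to identify composite measures most useful to assess response and remission in clinical practice".

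Section 5.0 explains why response needs a baseline criterion: "response can only be assessed in patients impaired when initiating the treatment". Section 5.2.1 (Response) carries this into the composites: "Eligibility criteria for impairment at biologic initiation and individual domain response definitions described in section 5.1 will be applied". As a result:

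- Composite 1 (exacerbations, long-term OCS) requires at least 2 exacerbations in the prior year and long-term OCS at initiation.
- Composite 2 adds symptom control, and requires patients to be partly controlled or uncontrolled at baseline.
- Composite 3 adds lung function, and requires baseline FEV1 below 80% predicted.

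Table 5 in section 6.2 gives the resulting preliminary counts as 313, 264 and 134. Its caption says that the "numbers presented are patients who were impaired at biologic initiation and with available data at follow-up".

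Section 6.4 computes response proportions "for each individual domain and composite definition of response". It then describes patient characteristics by response level and fits ordinal or binary logistic models to the composite levels. It stratifies the descriptive part by pre-biologic status, with no exacerbation and no long-term OCS use as examples, and plans pre- to post-biologic cross-tabulations. It names no analysis in which two or more composites are computed in the same patients.

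**The concern.** To say which composite is more useful, one has to set the composites side by side. As planned, two things change at each step: the rule that classifies a patient, and the patients being classified. If composite 3 gives a different level distribution from composite 1, or a characteristic is associated with level under one and not the other, the reader cannot tell which change produced it.

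The regressions are exposed as well. Characteristics enter the multivariate model if p<.05 in the univariate analysis. Other things equal, standard errors at n=134 are about sqrt(313/134) = 1.53 times those at n=313. A characteristic could thus be selected for composite 1 and not for composite 3 because of sample size or patient mix, with no bearing on the merit of the definition.

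**Working it through.** **Inputs.** Table 5: N = 313 (domains 1+2), 264 (1+2+3), 134 (1+2+3+4); single-domain counts 1,392, 475, 1,360 and 1,179. The protocol gives no response rates by subset, so the gaps below are assumptions shown as a range.

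**Consistency of the plan's own counts.** These are database counts, not the output of a formula, so they can be checked only for coherence. Each composite's eligibility is the previous one plus one further condition, so the sets must be nested and must shrink. 313 does not exceed the smaller of 1,392 and 475, and 313 ≥ 264 ≥ 134. Both hold. Nesting assumes that available follow-up data in Table 5 means data in every domain of the composite concerned.

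**Patients lost at each step.**

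- Composite 1 to 2: 313 − 264 = 49; 49/313 = 15.7%.
- Composite 2 to 3: 264 − 134 = 130; 130/264 = 49.2%.
- Composite 1 to 3: 313 − 134 = 179; 179/313 = 57.2%.

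No new patients enter at any step. The losses combine patients not impaired in the added domain with patients lacking data for it, and Table 5 does not separate the two.

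**Shift from selection alone.** Hold the definition fixed, for example the proportion meeting both composite 1 criteria. Let p_r be that proportion in the retained patients and p_l in the lost patients. For 313 against 134:

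p313 = (134·p_r + 179·p_l)/313, so |p_r − p313| = (179/313)·|p_r − p_l|.

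In general, the shift is the share lost times the gap:

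| Assumed gap (points) | 313 vs 264 | 313 vs 134 |
|---|---|---|
| 5 | 0.8 | 2.9 |
| 10 | 1.6 | 5.7 |
| 20 | 3.1 | 11.4 |
| 30 | 4.7 | 17.2 |

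One case in full: with 45% in the 134 and 55% in the other 179, p313 = (134×0.45 + 179×0.55)/313 = 158.75/313 = 50.7%. That is 5.7 points from the 45% in the common set, with no change of definition.

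**Does the planned stratification remove this?** Its example strata (no exacerbation, no long-term OCS use) are empty in all three composites, since every patient has at least 2 exacerbations and receives long-term OCS. The criteria that take 313 down to 134 are symptom control and FEV1, which the examples do not mention. The stratification is attached to the descriptive analysis, not to the models. The cross-tabulations follow patients from before to after initiation and do not set one definition against another.

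**Precision in a common set.** 95% half-width = 1.96·sqrt(p(1−p)/n), at an assumed p = 0.5: ±5.5 points at n=313, ±6.0 at n=264, ±8.5 at n=134.

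**The case against.** The strongest defence is that no contrast between composites is planned. The objectives and section 6.4 compare patient characteristics between levels within each composite. Domain-specific eligibility is deliberate, explained in section 5.0 and disclosed in Table 5. This stands in part: there is no formal test to invalidate, and separating definition from selection is not itself the wording of the aim. But a judgement of which composite is most useful cannot be reached without comparing them, even informally.

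It can also be said that such tables belong in a statistical analysis plan, which is not at hand. The protocol itself, however, fixes the composite-specific eligibility, the counts and the per-composite analyses, and the point is what those choices allow the aim to conclude.

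A third argument is that in a fixed set, meeting all criteria can only become rarer as criteria are added. That is true of the direction. It does not determine how large the fall is or which patients are reclassified, and those are what the comparison should show.

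Stronger readings are tempting but not supported:

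- *That the study cannot separate definition from selection.* The sets are nested, so its own data allow it. This is a gap in the planned analysis, not a limit of the design.
- *That remission has the same problem.* Section 5.2.1 (Remission) states: "Composite definitions of remission will not impose pre-biologic impairments in any domains". The counts 313, 264 and 134 do not apply there. Remission denominators could still differ through data availability, but the flowchart in Figure 2 is not shown and this cannot be judged.
- *That the four-domain set should replace the planned sets as the main analysis.* It holds only 134 patients, all on long-term OCS, and would narrow a study meant to reflect real-world practice.

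**Conclusion.** The point holds for the three main response composites. As planned, differences between them in response proportions or associated characteristics mix the definition with patient selection. The step from composite 1 to 2 is minor; adding lung function is the step that matters, since it removes about half of the remaining patients.

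The size in percentage points is not known. The range of 2.9 to 17.2 points for 313 against 134 rests on assumed gaps of 5 to 30 points, and the shift is zero if retained and lost patients respond alike. The counts are labelled preliminary, so the shares lost may change in the final dataset. This is a cheap improvement that should be made before the composites are ranked; it does not undermine the within-composite analyses.

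**What to change.** Keep the definition-specific analyses as they are and add to section 6.4:

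1. All three response composites computed in the common set of patients impaired, and with data, in all four domains (about 134).
2. Composites 1 and 2 computed in their common set (about 264).
3. In each common set, a cross-tabulation of the level each patient receives under each definition, showing at least who reaches the top level under one definition and not another.
4. A sentence stating that conclusions about which response definition is more useful will rest on this comparison.

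The cost is a few extra tables on existing data. Intervals widen to about ±8.5 points at n=134, against ±5.5 at n=313 (assuming 50%), and more when split by biologic class. Results from the four-domain set apply only to patients impaired in all four domains, which is why the definition-specific analyses should stay.
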